Treatment scheme	
Primary Treatment Phase
 
Treatment will continue until PD or unacceptable toxicity, death, withdrawal of consent by the patient, or non-compliance by the patient with protocol requirements.
 
Each cycle is 28 days (4 weeks) long. In twice-weekly dose schedules (i.e., Part 1 and Part 2, Schedule 1), 8 doses of selinexor will be administered per cycle. In the once-weekly dose schedule (i.e., Part 2 Schedule 2), 4 doses of selinexor will be administered per cycle. Twice-weekly doses of selinexor must be administered at least 36 hours apart; once-weekly doses of selinexor must be administered at least 5 days apart.

	
Dose escalations and reductions/interruptions are permitted according to safety guidelines in this protocol or in consultation with a sponsor representative.
 
Part 1: Patients will receive oral selinexor 50 mg/m² twice weekly (e.g., Monday and Wednesday, Tuesday and Thursday, Wednesday and Friday or Thursday and Saturday) in each week of a 4-week cycle.
 
If the patient has not experienced a major toxicity after 12 weeks of treatment, a selinexor dose escalation to 60 mg/m² twice weekly will be allowed.
 
Dose reductions (minimum dose: 35 mg/m² once weekly) and interruptions are permitted.
 
Part 2:
 
Schedule 1
 
Patients will receive oral selinexor 35 mg/m² twice weekly (e.g., Monday and Wednesday, Tuesday and Thursday, Wednesday and Friday or Thursday and Saturday) in each week of a 4-week cycle.
 
If there has been no major toxicity after 6 weeks, a dose escalation to 50 mg/m² twice weekly in each week of a 4-week cycle will be allowed.
 
Schedule 2
 
Patients will receive oral selinexor 50 mg/m² once weekly in each week of a 4-week cycle (e.g., Monday of each week).
 
If the patient has not experienced a major toxicity after 6 weeks of treatment, a dose escalation to 60 mg/m² once weekly will be allowed.
 
Dose reductions (minimum doses - Schedules 1 and 2: 35 mg/m² once a week) and interruptions are permitted.
 
Maintenance Phase
 
See Section 18 (Appendix 16) for the schedule of assessments for the Maintenance Phase of the study to continue treatment with selinexor and/or survival follow-up under Version ≥3.2 of the protocol.

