3.1.1 Definition of Treatment Cycle and Duration

Each cycle is 28 days (4 weeks) long. In twice-weekly dose schedules (i.e., Part 1 and Part 2, Schedule 1), 8 doses of selinexor will be administered per cycle. In the once-weekly dose schedule (i.e., Part 2 Schedule 2), 4 doses of selinexor will be administered per cycle. Twice-weekly doses of selinexor must be administered at least 36 hours apart; once weekly doses of selinexor must be administered at least 5 days apart.

Dose escalations and reductions/interruptions are permitted according to safety guidelines in this protocol or in consultation with a sponsor representative (see Section 6.3).

Dose schedules in Parts 1 and 2 are as follows:

- **Part 1:** Patients will receive oral selinexor 50 mg/m² twice weekly (e.g., Monday and Wednesday, Tuesday and Thursday, Wednesday and Friday or Thursday and Saturday) in each week of a 4-week cycle.

- **Part 2:**
 - *Schedule 1* – Patients will receive oral selinexor 35 mg/m² twice weekly (e.g., Monday and Wednesday, Tuesday and Thursday, Wednesday and Friday or Thursday and Saturday) in each week of a 4-week cycle.
 - *Schedule 2* – Patients will receive oral selinexor 50 mg/m² once weekly in each week of a 4-week cycle (e.g., Monday of each week).

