Grade 4	Discontinue selinexor and rule out other causes. If other causes of grade 4 adverse event are uncovered, selinexor may be re-started at a reduced dose level	Discontinue selinexor and rule out other causes. If other causes of grade 4 adverse event are uncovered, selinexor may reduce in 2 dose level	Discontinue selinexor and rule out other causes. If other causes of grade 4 adverse event are uncovered, selinexor may be re-started at a reduced dose level.

All dose modifications should be based on the worst preceding toxicity.

Isolated values of ≥ grade 3 alkaline phosphatase values will NOT require dose interruption. Determination of liver vs bone etiology should be made, and evaluation of gamma-glutamyl transferase (GGT), 5'-nucleotidase (5'NT), or other liver enzymes should be performed.

≥ Grade 3 anemia judged to be a hemolytic process secondary to study drug will require interruption of study treatment until resolved to ≤ grade 1. Selinexor may then be re-instituted at 1 level below original dose (Table 2 and Table 3).

≥ Grade 3 lymphopenia considered clinically significant will require dose interruption until resolved to ≤ grade 2, then reduce by 1 dose level.

Patients are allowed dose reductions to a minimum dose of 35 mg/m² once weekly for Part 1 and Part 2 (Schedules 1 and 2) as described in Table 2 and Table 3, respectively.

If a patient requires a dose interruption of > 28 days, then the patient must be discontinued from the study. Patients who discontinue the study for a study-related adverse event or abnormal laboratory value must be followed at least once a week for 28 days and subsequently at 28-day intervals until resolution or stabilization of the event, whichever comes first.

Common Terminology Criteria for Adverse Events (CTCAE Version 4.03) or otherwise specified values.

^aNational Comprehensive Cancer Network[®]. NCCN Clinical Practice Guidelines in Oncology (NCCN Guidelines[®]): Fatigue. Available at http://www.nccn.org/professionals/physician_gls/pdf/fatigue.pdf.

^bNational Comprehensive Cancer Network[®]. NCCN Clinical Practice Guidelines in Oncology (NCCN Guidelines[®]): Palliative Care, version 2.2015. Fort Washington, NY. May 2015. Available at: <http://www.nccn.org/content/nationalcontent/resourcecenter/freeeducationmaterials/generalcancer/pdf/facts.pdf>. Attached as Appendix 11.

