6.3.5 Missed or Vomited Doses

For once weekly dosing, a maximum of one dose may be given per week; for twice weekly dosing, a maximum of two doses may be given per week. Doses should not be administered less than 5 days apart for once weekly dosing and less than 36 hours apart for once weekly dosing. Every effort should be made to avoid missed doses.

Missed doses

Doses held due to AE(s) will not be considered missed.

Vomited doses

If a dose is vomited within one hour of ingestion, it will be replaced. If vomiting occurs more than 1 hour after dosing, it will still be considered a complete dose.

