#### 3.2. General Methods

All data listings that contain an evaluation date will contain a relative study day (Rel Day). Pre-treatment and on-treatment study days are numbered relative to the day of the first dose of study medication which is designated as Day 1. The preceding day is Day -1, the day before that is Day -2, etc. The last day of study medication is designated with an "L" (e.g., Day 14L). Post-treatment study days are numbered relative to the last dose and are designated as Day 1P, Day 2P, etc.

All output will be incorporated into Microsoft Word files, sorted and labeled according to the International Conference on Harmonization (ICH) recommendations, and formatted to the appropriate page size(s).

Tabulations will be produced for appropriate disposition, demographic, baseline, efficacy, and safety parameters. For categorical variables, summary tabulations of the number and percentage of patients within each category (with a category for missing data) of the parameter will be presented. For continuous variables, the number of patients, mean, median, standard deviation (Std Dev), minimum, and maximum values will be presented. Time-to-event data will be summarized using Kaplan-Meier (KM) methodology using 25th, 50th (median), and 75th percentiles with associated 2-sided 95% confidence interval (CI), as well as number and percentage of censored observations and events.

Data will be presented by study part, cohort, and schedule (Part 2 only) as follows:

- Part 1: Cohort A
- Part 1: Cohort B
- Part 1: Cohort C
- Part 2: Cohort A: Schedule 1
- Part 2: Cohort A: Schedule 2

Formal statistical hypothesis testing will be performed on the primary endpoint with all tests conducted at the one-sided 0.10 level of significance for Part 1 and at the two-sided 0.20 level of significance for Part 2. Summary statistics will be presented, as well as CIs on selected parameters, as described in the sections below.

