### 4.5.1. Study Drug Exposure

Study drug exposure will be determined by duration, percent compliance, total drug taken, and dose intensity, as described below.

Duration of study drug exposure will be calculated as the number of day patients were administered study drug, as determined below, and will be summarized by cohort using descriptive statistics. Duration of study drug exposure for each patient will also be provided in a data listing, along with number of cycles administered.

$$\text{Duration of Study Drug Exposure} = (\text{Date of last dose} - \text{Date of first dose}) + 1$$

Percent compliance will be summarized for each patient from date of first dose through the treatment period per the following definition:

$$\text{Percent Compliance} = \frac{\text{Amount of drug taken (mg)}}{\text{Amount of drug prescribed (mg)}} \times 100$$

Patient compliance with study drug will be summarized by cohort and presented in a by-patient data listing. Percent compliance will be summarized separately for patients who completed the study versus those who withdrew early (i.e. patient decided to discontinue study treatment, patient withdrew consent, or patient was withdrawn from treatment due to protocol violation) so as to distinguish between those patients who were compliant throughout the entirety of the study versus those who were compliant until they withdrew. In the listing, patients who withdrew from the study early will be flagged.

Total drug taken will be presented in mg, and calculated by a summation of all doses received. Total drug prescribed will be presented in mg, and calculated by a summation of all doses prescribed. For patients receiving a mg/m^2 dose, amount of drug prescribed will be calculated using baseline BSA calculated using the Dubois and Dubois formula listed in Section 4.2 (Dubois and Dubois, 1916).

Dose intensity (defined as total drug taken divided by duration of exposure, presented in mg/day and mg/week), number of missed doses, number of dose interruptions, duration of dose interruption, number of dose reductions, and number of dose escalations will also be summarized. Duration of dose interruption will be calculated as the number of days from the most recent dose prior to the interruption until the next dose received.

Dosing information for each patient will be presented in a data listing.

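### SAP 4.5.1 counts interruption length from the last dose taken, so it includes the planned dosing gap and holds of equal length read 2 or 5 days longer on once-weekly than on twice-weekly dosing

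*SAP*

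**What the plan says.** SAP 4.5.1 lists the exposure items to be summarised, among them "number of missed doses, number of dose interruptions, duration of dose interruption, number of dose reductions". It then gives the rule for interruption length: "calculated as the number of days from the most recent dose prior to the interruption until the next dose received". Neither that section nor any other visible text subtracts the scheduled interval, adjusts for schedule, or defines what counts as an interruption.

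Protocol 3.1.1 sets two dosing frequencies:

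- Part 2 Schedule 2: "once weekly in each week of a 4-week cycle (e.g., Monday of each week").
- The other regimens, Schedule 1 of Part 2 and the whole of Part 1, are described as "twice weekly (e.g., Monday and Wednesday, Tuesday and Thursday, Wednesday and Friday or Thursday and Saturday) in each week of a 4-week cycle".

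SAP 3.2 presents the two Part 2 schedules as separate groups ("Part 2: Cohort A: Schedule 1", and likewise Schedule 2), so the exposure summary will show them next to each other.

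Two protocol rules bear on how the summary is read. Section 6.3.5 states: "Doses held due to AE(s) will not be considered missed". The notes to Table 4 in section 6.3.2 set a consequence that begins "If a patient requires a dose interruption of > 28 days", and section 6.3 has a similar limit for a treatment delay of more than 4 weeks. Neither limit says from which day the count starts.

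**The concern.** A patient who took a dose on time and is waiting for the next one is on schedule. Interruption begins when a due dose is not given. By starting the clock at the last dose taken, the SAP labels planned off-drug days as interruption.

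A constant excess would matter little. Here it depends on the schedule, because the planned gap is 7 days on one and 2 or 5 days on the others. Part 2 was added to learn how the two dosing frequencies differ in efficacy and safety, with about 16 patients per schedule (Protocol 3.2). At that size much of the tolerability reading will rest on descriptive tables like this one. Doses held for adverse events are not counted as missed, so the missed-dose count need not capture them and the interruption summary has to carry that information.

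The same distortion can arise within one patient. Tables 2 and 3 of the protocol include reductions from twice-weekly to once-weekly dosing, so the planned gap built into the measure can change during treatment.

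**Working it through.** The plan gives no worked figure for this measure, so there is nothing to reproduce. The check is date arithmetic on the nominal calendars.

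**Inputs**

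- Once weekly (Protocol 3.1.1, Schedule 2): planned gap of 7 days.
- Twice weekly (Protocol 3.1.1, Part 1 and Schedule 1): each of the four example day pairs is 2 days apart within the week, which leaves 7 − 2 = 5 days to the next pair. The planned gap is 5 days before the first weekly dose and 2 days before the second.

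**Formulas**

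- SAP duration = date of next dose received − date of last dose taken.
- Duration from the due date = date of next dose received − date the first held or omitted dose was due.
- The difference between them is the planned gap before the first dose not given: 7 days once weekly; 5 or 2 days twice weekly.

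**Holds of equal length, measured from the first due dose**

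| Hold | From due date, all schedules | SAP rule, once weekly | SAP rule, twice weekly, first weekly dose held first | SAP rule, twice weekly, second weekly dose held first |
|---|---|---|---|---|
| 1 week | 7 | 7 + 7 = 14 | 5 + 7 = 12 | 2 + 7 = 9 |
| 2 weeks | 14 | 7 + 14 = 21 | 5 + 14 = 19 | 2 + 14 = 16 |
| 4 weeks | 28 | 7 + 28 = 35 | 5 + 28 = 33 | 2 + 28 = 30 |

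The once-weekly figure exceeds the twice-weekly one by 7 − 5 = 2 or 7 − 2 = 5 days at every hold length. Counting from the due date removes the difference.

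**One omitted dose**

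| | Once weekly | Twice weekly, first weekly dose omitted | Twice weekly, second weekly dose omitted |
|---|---|---|---|
| SAP rule | 7 + 7 = 14 | 5 + 2 = 7 | 2 + 5 = 7 |
| From due date | 7 | 2 | 5 |

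Under the SAP rule the ratio is 14/7 = 2.0. From the due date the twice-weekly mean is (2 + 5)/2 = 3.5, and 7/3.5 is again 2.0.

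**Against the 28-day wording.** A hold of exactly 28 days from the first due dose appears in the SAP summary as 30, 33 or 35 days. The protocol does not say that its own count starts at the first due dose, so this shows only that the two counts can differ by 2 to 7 days.

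**The case against.** The SAP rule is explicit and can be reproduced from actual dose dates, which Protocol 6.2.3 requires in the eCRF. Time from last dose to next dose is a legitimate quantity. The alternative needs a due date, which is less firm: dosing days are given only as examples, with minimum spacings ("once-weekly doses of selinexor must be administered at least 5 days apart"; 36 hours for twice weekly), and patients may change frequency during treatment. This stands as a cost of the change. It does not make the present figure an interruption length that can be read across schedules.

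The measure is also minor. It has no test, threshold or decision rule. Percent compliance, dose intensity and the missed-dose count do not use it, and each patient's dosing is listed, so a reader could recompute it. That stands in full. The output lists and table shells are redacted, so a working definition of interruption may exist there.

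Three stronger readings are tempting, and the documents do not support them:

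- A reader might infer that the rule makes one omitted dose look twice as long once weekly (14 against 7 days). The rule does not cause that ratio: it averages 2.0 from the due date as well, because one weekly dose covers twice the calendar time. A single omitted dose may not even be an interruption, since SAP 4.5.1 counts missed doses and interruptions separately.
- A reader might infer that Part 2 formally compares schedules on interruption length. The between-schedule analysis specified in SAP 4.3.1 and Protocol 8.4.3 is Fisher's exact test on disease control rate.
- A reader might infer that compliant patients would be reported as breaching the 28-day limit. That assumes a start point the protocol does not state, and the SAP summary is not said to audit that limit.

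**Conclusion.** The point holds in a limited form. The SAP rule overstates each interruption by the planned dosing gap: 7 days once weekly, 2 or 5 days twice weekly. Holds of equal length therefore read 2 or 5 days longer on Schedule 2 than on the twice-weekly schedules. In relative terms this matters most for short holds (14 against 12 or 9 days for one week) and less for long ones (35 against 33 or 30 for four weeks).

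The figures assume the nominal weekly calendar and the protocol's example day pairs. Drift within the allowed spacing would make them approximate. The consequence is confined to a descriptive exposure summary, and efficacy results are unaffected. It is worth correcting because the rule is explicit, the error depends on schedule, and the correction is cheap.

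Separately, the SAP count and the protocol's 28-day and 4-week wording share no stated start point, so the summary cannot be read directly against those limits.

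**What to change.** Replace the sentence in SAP 4.5.1 with: duration of dose interruption is the date of the next dose received minus the date on which the first held or omitted dose was due, under the dosing schedule in force for that patient when the dose was held.

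In the same edit, say what counts as an interruption, and whether a single omitted dose does.

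State also how this count relates to the protocol's 28-day interruption wording (6.3.2) and 4-week delay wording (6.3), so that the passages are reconciled. Which start point the clinical limits should use is for the sponsor to settle.

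The cost is one or two SAP sentences and a derived due date in the exposure dataset. Dose dates, missed doses and dose modifications are already to be recorded (Protocol 6.2.3 and 6.3). The added work falls on patients whose dosing days or frequency have changed, for whom the due date must be derived from the schedule then in force. If the sponsor prefers to keep the last-dose-to-next-dose figure, it should be labelled as a dosing gap and shown beside the corrected duration.

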## Relevant Output

CCI

### 4.5.2. Adverse Events

AEs will be coded using the MedDRA dictionary and displayed for all study patients combined, in tables and listings using System Organ Class (SOC) and Preferred Term.

Analyses of AEs will be performed for those events that are considered treatment emergent, where treatment-emergent is defined as any AE with onset or worsening of a pre-existing condition on or after the first administration of study medication through 30 days following last dose or any event considered drug-related by the investigator through the end of the study. AEs with partial dates will be assessed using the available date information and will first be imputed according to the rules outlined in Section **Error! Reference source not found.** to determine if treatment-emergent; AEs with completely missing dates will be assumed to be treatment-emergent.

Adverse events will be summarized by patient incidence rates, therefore, in any tabulation, a patient contributes only once to the count for a given AE preferred term.

An overall summary of AEs will be provided and will include the number and percentage of patients with any treatment-emergent AE (TEAE), further separated by maximum severity, with at least one treatment-related TEAE, with any TEAE with a CTCAE severity Grade  $\geq 3$ , with any treatment-emergent SAE, with any treatment-related (determined by the Investigator as possibly related or related) treatment-emergent SAE, with any TEAE leading to discontinuation of study drug, and with any TEAE leading to death will be presented. In these tabulations, each patient will contribute only once (i.e., the most related occurrence or the most intense occurrence) to each of the incidence rates in the descriptive analysis, regardless of the number of episodes.

Additional summary tables by SOC and preferred term include all TEAEs, TEAEs assessed by the Investigator as related to treatment, treatment-emergent SAEs, non-serious TEAEs, TEAEs by CTCAE severity grade, and TEAEs with a CTCAE severity grade  $\geq 3$ . Common TEAEs occurring in  $\geq 10\%$  of the overall safety population will be presented by preferred term, in descending frequency, by cohort and overall.

[figure not shown]
No formal hypothesis-testing analysis of AE incidence rates will be performed.

All AEs (treatment emergent and post-treatment) occurring on-study will be listed in patient data listings.

By-patient listings will also be provided for the following: AEs leading to death, SAEs, and AEs leading to discontinuation of study medication.

Relevant Output

CCI

#### 4.5.3. Laboratory Data

Clinical laboratory values will be expressed in International System of Units (SI) units.

The actual value and change from baseline (Day 1, or in general, the last evaluation prior to initiation of study treatment) to each on-study evaluation will be summarized for each clinical laboratory parameter, including hematology, clinical chemistry, coagulation, and urinalysis, for all study patients combined. In the event of repeat values, the last non-missing value per study day/time will be used. In the event that Day 1 data are unavailable for a given patient/parameter, the Screening value will substitute as the baseline value.

[figure not shown]
Severity of select clinical laboratory measures will be determined using CTCAE criteria (e.g. those measures that have a corresponding CTCAE grade classification). Shift tables that present changes from baseline to worst on-study values relative to CTCAE classification ranges will be produced. Unscheduled visits will not be included in the laboratory summaries, other than the shift table for worst on-study values.

All laboratory data will be provided in data listings.

A subset listing will be presented for all clinically significant and abnormal laboratory values. Laboratory values with a CTCAE toxicity grade  $\geq 3$  will also be presented in a subset listing and summary table.

Relevant Output

CCI

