7.1.3 Laboratory Test Abnormalities

Laboratory test results will be recorded on the laboratory results pages of the eCRF. In the event of unexplained abnormal laboratory test values, the tests should be repeated and followed up until they have returned to the normal range and/or an adequate explanation of the abnormality is found.

Laboratory test value abnormalities as such should not be reported on the AE page of the eCRF as adverse events unless they are treatment-emergent and they satisfy one or more of the following conditions for clinical significance:

1. Accompanied by clinical symptoms
2. Leading to a change in study medication (e.g., dose modification, interruption or permanent discontinuation)
3. Requiring a change in concomitant therapy (e.g., addition of, interruption of, discontinuation of, or any other change in a concomitant medication, therapy or treatment)

Please note: Any laboratory result abnormality fulfilling the criteria for a serious adverse event (SAE) should be reported as such, in addition to being recorded as an adverse event in the eCRF.

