  15. Coagulation-test includes prothrombin time (PT), international normalization ratio (INR), and activated partial thromboplastin time (aPTT). This will be performed at baseline and if clinically indicated. Blood draw can be done up to 3 days prior to visit.
  16. CT/MRI of abdomen must include pelvis. PET-CT is allowed, but ultrasound of the abdomen and x-ray of thorax is not allowed. CT/MRI or PET/CT scans to be performed within four weeks prior to registration. CT scan is required again if patient has relapse and if clinically justified during trial period. On-study tumor assessment should be performed after 6 weeks ( $\pm$  7 days) and 12 weeks ( $\pm$  7 days) of treatment. Thereafter, tumor assessments will be performed every 8 weeks ( $\pm$  7 days) thereafter, independent of cycle delays, until disease progression or death.
  17. Patients to complete the EORTC QLQ-C30 at baseline, with tumor assessment during treatment (i.e. at Week 6, Week 12 and every 8 weeks thereafter), and at the End of Treatment visit.
  18. Selinexor dosing for Part 1, and Part 2, Schedule 1: Twice weekly (e.g., Monday and Wednesday, Tuesday and Thursday, Wednesday and Friday or Thursday and Saturday) in each week of a 4-week cycle; Part 2, Schedule 2: Once weekly dosing in each week of a 4-week cycle (e.g., Monday of each week). For dosing details, including delayed doses and changes to the visit schedule, see Protocol Section 6.2.2 and Section 6.3).
  19. All patients will receive required supportive care to prevent nausea, as described in Protocol Section 6.5.1.
- CCI
- CCI
23. After treatment discontinuation, a call will be made to the patient (or the patient's family) approximately every 3 months to inquire about the patient's survival status.

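### As worded, the SAP's Grade ≥3 laboratory summary table leaves out severe values seen only at unscheduled visits, and can disagree with the shift table

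*SAP*

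**What the plan says.** SAP 4.5.3 (Laboratory Data) sets out these laboratory outputs in order:

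- Actual values and changes from baseline at each on-study evaluation, "including hematology, clinical chemistry, coagulation, and urinalysis, for all study patients combined".
- CTCAE shift tables: "Shift tables that present changes from baseline to worst on-study values relative to CTCAE classification ranges will be produced". The paragraph closes with the rule at issue: "Unscheduled visits will not be included in the laboratory summaries, other than the shift table for worst on-study values".
- Listings: "All laboratory data will be provided in data listings".
- Laboratory values of CTCAE Grade ≥3, which "will also be presented in a subset listing and summary table".

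The worst-value shift table is the only exception the SAP names.

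On timing, SAP Table 1-1 schedules haematology and clinical chemistry at baseline, on Day 1 and Day 15 of each 28-day cycle, and at end of treatment. Coagulation is marked at baseline only, and its footnote says: "This will be performed at baseline and if clinically indicated".

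Protocol 8.4.4.2 has no exclusion of unscheduled visits. It plans a listing, not a summary table, for Grade ≥3 laboratory values, and it does not name coagulation among the parameters to be summarised.

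**The concern.** Leaving unscheduled visits out of by-visit means and changes is ordinary practice, because those results have no common time point. A count of severe values is different. Its purpose is to show how many patients reached Grade ≥3 at any time, and the visit at which that happened is irrelevant. Under the wording of 4.5.3, a programmer would apply the unscheduled-visit filter to the Grade ≥3 summary table as well, because the author considered exceptions and named only one.

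A reader who wants the incidence of severe laboratory toxicity will go to the Grade ≥3 table. If that table shows fewer patients than the shift table in the same report, with no stated reason, the reader cannot tell which number is the incidence. The error can only run one way, towards fewer severe values.

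**Working it through.** No plan figure needs reproducing here. The check sets the rule beside the displays and the schedule.

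**Step 1. Which displays contain an unscheduled Grade ≥3 value, on the literal text?**

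| Display in SAP 4.5.3 | Exempted from the exclusion? | Unscheduled Grade ≥3 value appears? |
|---|---|---|
| By-visit actual value and change | No | No |
| Shift table, baseline to worst | Yes, by name | Yes, if it is the worst value |
| Grade ≥3 summary table | No | No |
| Grade ≥3 subset listing | Not a summary | Yes |
| Full laboratory listings | Not a summary | Yes |

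**Step 2. Direction of the discrepancy.** For one parameter, let S be the patients with a post-baseline Grade ≥3 value at a scheduled visit, and A the patients with such a value at any visit. The Grade ≥3 table counts S, and the shift table's worst-value column reflects A. Since S is contained in A, the difference A − S is the number of patients whose Grade ≥3 values all came from unscheduled visits. It is zero or positive, never negative. As an illustration, take a patient at Grade 1 on Day 1, Grade 3 on an unscheduled draw, and Grade 2 on Day 15. The shift table shows worst Grade 3, and the Grade ≥3 table omits her. This assumes that the table counts patients; if it counts values, the omission is of values.

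**Step 3. Are unscheduled draws to be expected?** Scheduled haematology and chemistry come twice per 28-day cycle, about 28/2 = 14 days apart. Several protocol rules imply sampling between or after those visits:

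- In Protocol 6.3.2, Table 4, the Grade 4 neutropenia rule turns on whether recovery takes up to 7 days or longer.
- The notes to that table say that patients who stop for a study-related adverse event or "abnormal laboratory value must be followed at least once a week for 28 days and subsequently at 28-day intervals".
- Protocol 7.1.3 says that for unexplained abnormal results "the tests should be repeated and followed up until they have returned to the normal range".

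So such draws will exist. How often one of them supplies a patient's only Grade ≥3 value is not stated anywhere.

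**Step 4. Do the adverse event tables fill the gap?** Only partly. Under Protocol 7.1.3, a laboratory abnormality that does not meet seriousness criteria is recorded as an adverse event only if it is treatment-emergent and is symptomatic, changes study medication, or changes concomitant therapy. Table 4 keeps the dose level for neutropenia up to Grade 3. An asymptomatic Grade 3 neutropenia that led to no change in concomitant therapy therefore need not appear in any adverse event table.

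**Step 5. Coagulation.** SAP Table 1-1 has 0 scheduled post-baseline coagulation time points in the Primary Treatment Phase. The Maintenance Phase schedule (Protocol Appendix 16, Table 11) does include coagulation, but those data go to a separate database and SAP Table 1-1 does not cover that phase. SAP 3.11 tabulates data under the visit recorded on the eCRF, and the 4.5.3 rule excludes unscheduled visits rather than unscheduled tests. A clinically indicated coagulation test recorded under Day 1, Day 15 or end of treatment is therefore still summarised. What the by-visit summary can contain is whatever happened to be drawn for clinical reasons at those visits.

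**The case against.** The strongest reply has four parts.

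*The rule may not reach the Grade ≥3 table.* The exclusion closes the paragraph on grading and shift tables. The Grade ≥3 output is specified two paragraphs later, with no restriction of its own, in the same sentence as its listing. The relevant-output lists and table shells are redacted, so the programmed rule cannot be seen. This is a fair caution. But the sentence covers laboratory summaries generally and the Grade ≥3 output is called a summary table, so the body text points to exclusion. If a shell says otherwise, the body text contradicts it and still needs correcting.

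*Nothing is hidden.* The listings hold every value, the shift table holds the worst one, and the Grade ≥3 adverse event tables in SAP 4.5.2 carry no visit restriction. This stands and limits the harm. It does not make the Grade ≥3 laboratory table correct, and Step 4 shows that the adverse event tables are not a full substitute.

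*No protocol commitment is reduced.* The protocol promised only a listing of Grade ≥3 values and left analysis details to the SAP, which added the summary table and coagulation. This also stands. A reader might infer an undeclared departure from the protocol, but part of SAP section 5 is redacted, so its silence proves little.

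*The cited follow-up rules start from an abnormality already found.* This is true of the repeat-testing rule and the weekly follow-up rule. They show that unscheduled draws occur, not that the first or worst severe value usually comes from one.

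**Conclusion.** The point holds in a limited form. On the literal text of SAP 4.5.3, the Grade ≥3 laboratory summary table omits severe values found only at unscheduled visits and can show fewer patients than the shift table. The direction is certain; the size cannot be derived from the documents. The conclusion rests on reading the sentence as written and on no contrary rule in the redacted shells.

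For coagulation, there is no scheduled on-study time point in the Primary Treatment Phase, so the planned by-visit summary would be sparse and driven by clinical indication.

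Three stronger readings are tempting and are not supported:

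- *That the coagulation summary has no on-study data, or that all on-study values are excluded.* Tests recorded under scheduled visits are tabulated. Protocol 6.4.1.2 also has patients on warfarin monitored for INR twice a week in the first two cycles, and some of those dates can coincide with scheduled visits.
- *That a stated share of severe episodes is lost.* With draws every 14 days and an episode of L days starting at random, a scheduled draw catches L/14 of episodes: 5/14 = 36%, 7/14 = 50%, 10/14 = 71%, leaving 64%, 50% and 29%. Those episode lengths come from no document, and the remainder includes episodes that nobody sampled, which no SAP wording could recover. The figures are a ceiling on missed episodes under that assumption, not the undercount in the table.
- *That the omission narrows the tolerability contrast between the Part 2 schedules.* This is conceivable, but the documents give no rate of unscheduled draws by schedule.

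**What to change.** In SAP 4.5.3, replace the exclusion sentence with:

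> Unscheduled values are excluded only from the by-visit actual-value and change-from-baseline summaries; they are included in the Grade ≥3 summary table, the shift tables and all worst-value displays.

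Summarise coagulation as baseline versus worst on-study value, including unscheduled results, and check that the shell for the Grade ≥3 table carries the same rule.

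The cost is a short text edit and a minor programming change. No new data are needed and nothing in patient management changes. The downside for the sponsor is that Grade ≥3 counts may become slightly less favourable.
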